8.0 SURGERY

- 8.1 The extent of surgical resection shall be documented as a) biopsy, or b) subtotal resection or c) gross total tumor resection as described by the operative report and by postoperative imaging.
- 8.2 If post-radiation imaging demonstrates changes concerning for tumor progression versus treatment-related change and the clinical situation warrants, a biopsy or repeat resection for diagnostic and/or therapeutic purposes may be performed at physician discretion as per standard clinical practice. Surgery would be performed as part of standard care and is not part of this study. Hospitalization for this procedure (part of routine clinical practice) may not be considered an SAE.
- 8.3 O⁶-methylguanine-DNA methyltransferase (MGMT) promoter methylation status and IDH-1 (assessed as part of standard practice) will be documented.

9.0 OTHER THERAPY (WHICH IS STANDARD FOR PATIENTS WITH GBM)

- 9.1 Steroids and anti-seizure medications may be given as clinically indicated. The total dose must be recorded pre-treatment, and at the time of each treatment evaluation. Steroids will be used in the smallest dose that will afford the patient satisfactory neurologic function and the best possible quality of life.
- 9.2 Prophylactic pneumocystis jirovecii pneumonia (PCJ) prophylaxis is a matter of physician judgment. If prophylaxis is offered during the concurrent phase, the use of monthly aerosolized pentamidine is recommended.
- 9.3 Analgesics and any other medications are to be specified and their dose recorded.
- 9.4 Data will be collected (for example, start date, total duration) on whether patients receive Novo-TTF (Optune) after radiation therapy, which is part of standard treatment for patients with GBM

10.0 PATIENT ASSESSMENTS

10.1 Study Plan

- 10.1.1 Patients will receive concomitant temozolomide (75 mg/m² daily for 6 weeks) with radiotherapy as per standard of care.
- 10.1.2 Temozolomide will be taken orally prior to RT. The physician will discuss with the patient any eating restrictions, when other medications should be taken, and when temozolomide should be taken on the days without RT as per standard of care.
- 10.1.3 Adjuvant temozolomide 150-200 mg/m² D1-5 q28 days (+/- 5 days) for six cycles will be started approximately 4 weeks following completion of radiotherapy. Additional cycles may be continued at investigator's

- discretion. The first cycle will be prescribed at 150 mg/m², then increase to 200 mg/m² at cycle 2, toxicity permitting, as per standard of care.
- 10.1.4 Patients will receive RT at the University of Michigan or one of its affiliate centers. The patient will be considered eligible to receive concurrent and adjuvant chemotherapy through outside physicians closer to his/her home with continued follow-up at the University of Michigan per study guidelines

10.2 Study Specific Calendar	Pre-Ry		Prior to Each Chemotherapy Cycle	Follow-up Evaluation ^{a,g}					
			-			Mon	th		
				1	3	5	7	13	19
History & Physical Exam	X			Х	Х	X	X	X	Χ
KPS & Neurological Exam	х	x ^b (wk 6 of RT		x	х	x	X	X	X
QOL Evaluation/MDASI/MMSE ^c	х	x ^c (wk 6 of RT)		x	х	х	Х	X	Х
CBC w/ Diff, Platelets	Х	Xq	$\mathbf{X}_{\mathbf{q}}$						
Comprehensive metabolic panel	x		\mathbf{x}^{d}						
Neurocognitive evaluation	x b			x			Х		X
Gadolinium enhanced Brain MR ^e	Х			Х	Х	Х	х	Х	х
Advanced MRI	х	X ^f (wk 4 of RT)			x ^f				
11C MET PET	X ⁱ (optional)	X ^f (wk 4 of RT)							
Toxicity Notation	х	Х		Х	х	X	X	X	Х

- a) Timing of follow ups (1 month = 28 days): As per standard of care, patients will typically be seen in follow-up 1 month after completion of chemoradiation, then every 2 months +/- 2 week window. At the physician's discretion, after the first 6 months, follow-up visits may be approximately every 3 months. If a patient's temozolomide cycles are prolonged due to time for blood count recovery or other factors, assessments may be delayed in accord with the temozolomide cycles. At follow-up visits, history and physical exam, KPS and neurologic exam, and toxicity evaluations will be undertaken.
- b) KPS and recording of steroid and anticonvulsant dose will be required during week 6 of radiotherapy. NANO evaluation will be required at baseline

- and at the time of advanced imaging follow-up (3 months post-RT and/or at the time of suspected progression).
- c) QOL/MDASI/MMSE evaluations will be undertaken at baseline, , 6 weeks (end RT), 1 month, 7 month, 13 month, 19 month (+/- 6 weeks) after the end of chemoradiation, typically at the time of standard clinical follow-up and preferably close to the date of imaging if imaging is obtained. Neurocognitive evaluation will be undertaken at baseline, 1 month, 7 months, and 19 months after chemoradiation (+/- 6 weeks).
- d) CBCD to be drawn weekly during radiation, and prior to every cycle of adjuvant chemotherapy, beginning with first cycle as per standard of care. Comprehensive metabolic panel will be drawn at least every 8 weeks, or more frequently at primary oncologist's discretion, as per standard practice.
- e) Clinical gadolinium enhanced MRI brain scans will be obtained as per standard clinical practice approximately every 8 weeks after chemoradiation, or per the treating physician's discretion as per standard practice.
- f) Up to 10 patients will optionally receive MET PET during Wk 4. All patients will receive advanced MRI (see appendix for details) at Wk 4 (between fractions 17-20), and an additional advanced MRI scan will be obtained 3 months (+/- 1 week) after completion of chemoradiation and/or at the time of suspected tumor recurrence.
- g) Patients will be followed for tumor progression and survival for up to 5 years from the end of radiotherapy. Tumor progression and date and cause of death will be documented, if known. Studies available in the clinical setting may also be used for study purpose as indicated under study aims.
- i) Only the first 30 patients total will optionally receive pre-radiotherapy MET PET

10.3 Evaluation during Study

- 10.3.1 A neurologic examination including NANO evaluation, performance status, Folstein MMSE, QOL questionnaires and symptom survey shall be performed according to the Study Calendar schedule (10.2).
- 10.3.2 A contrast enhanced MRI of the brain shall be obtained prior to radiotherapy as part of standard care. Clinical brain MRI will be obtained as part of standard follow-up as stated in the study calendar above. Additional MRI and MR spectroscopy (if elected and clinically indicated) studies may be obtained at times of neurologic deterioration to document tumor progression versus radiation necrosis.
- 10.3.3 Standard clinical time points for laboratory evaluation will be employed. Standardly, weekly blood counts shall be obtained while radiation with concomitant chemotherapy is administered. During adjuvant chemotherapy, CBCPD will typically be obtained at day 22 of the cycle

(nadir) and the day of/prior to each chemotherapy cycle, and as required based on hematological toxicity in prior cycles.

10.4 Criteria for Removal from Study

- 10.4.1 All patients will be followed for survival, and for progression of neurological symptoms and for evidence of treatment failure by MRI. Patients who have tumor progression, as defined below, will not be removed from the protocol and will continue to be followed endpoints including survival, salvage therapies, etc. Date and cause of death will be documented, if known.
- 10.4.2 Therapy may be discontinued at any time by the request of the patient.

10.5 Evaluation Criteria and Endpoints

Standard RANO criteria will be used primarily to evaluate objective tumor response. Measurable disease is defined as bi-dimensionally contrast-enhancing lesions with clearly defined margins by CT or MRI scan. Non-measurable disease is defined as either uni-dimensionally measurable lesions, masses with margins not clearly defined, or lesions with maximal perpendicular diameters less than 10 mm. Formal RANO assessments for the following time points will be obtained after baseline assessment: approximately 1 month, 3 months, 7 months, and 13 months after chemoradiation.

- 10.5.1 Complete Response (CR): Complete response requires all of the following including complete disappearance of all enhancing measurable and non-measurable disease sustained for at least 4 weeks; no new lesions; stable or improved non-enhancing (T2/FLAIR) lesions; and patient must be off corticosteroids or on physiologic replacement doses only, and stable or improved clinically.
- 10.5.2 Partial Response (PR): Partial response requires all of the following: ≥ 50% decrease, compared with baseline, in the sum of products of perpendicular diameters of all measurable enhancing lesions sustained for at least 4 weeks; no progression of non-measurable disease; no new lesions; stable or improved non-enhancing (T2/FLAIR) lesions on same or lower dose of corticosteroids compared with baseline scan; and patient must be on a corticosteroid dose not greater than the dose at time of baseline scan and is stable or improved clinically.
- 10.5.3 Stable Disease (SD): Stable disease occurs if the patient does not qualify for complete response, partial response, or progression (see next section) and requires the following: stable non-enhancing (T2/FLAIR) lesions on same or lower dose of corticosteroids compared with baseline scan and clinically stable status.

10.5.4 Progression (PD) is defined by any of the following: ≥ 25% increase in sum of the products of perpendicular diameters of enhancing lesions (compared with baseline if no decrease) on stable or increasing doses of corticosteroids; a significant increase in T2/FLAIR non-enhancing lesions on stable or increasing doses of corticosteroids compared with baseline scan or best response after initiation of therapy, not due to comorbid events; the appearance of any new lesions; clear progression of non-measurable lesions; or definite clinical deterioration not attributable to other causes apart from the tumor, or to decrease in corticosteroid dose. Failure to return for evaluation as a result of death or deteriorating condition should also be considered as progression.

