We anticipate enrolling 40 patients eligible to undergo a boost of radiation (>1 cc combined high b-value DW-MRI and perfusion MRI abnormality) at our institution. A similar protocol will be opened at a second center and treat an additional 40 patients in an identical fashion. This approach was chosen over a single multi-institutional trial protocol for logistical and financial reasons. Nevertheless, we expect to jointly analyze the data from all 80 patients following trial completion. Center will be included as a stratification variable in the analyses. Allowing for 10% of these patients to be non-evaluable for the primary endpoint, 40 (80) enrolled patients will provide greater than 80% power to detect an improvement in 12 month OS from 65% (based on historical controls) to 82% (40 patients) or 78% (80 patients). These results are based on an exact 1-sided test at alpha=0.10. Once completed, this trial will determine if the treatment is sufficiently promising to warrant further investigation in a multi-center, randomized trial.

11.2 Secondary objective: To estimate progression-free survival, patterns of failure and response rates in relation to values from historical control patients.

Progression Free Survival is defined as the time from study enrollment till the first of death from any cause or progression. Kaplan-Meier estimates of PFS will be generated for all patients on this trial and according to MGMT/IDH1 status. Additionally we will compare the observed PFS at 6 months and 1 year to published values from historical control patients.

Patterns of failure and response rates - Failures will be classified as central, in-field, marginal or distant, based on previously published criteria. Our hypothesis is that including high b-value diffusion and perfusion MRI in treatment planning will reduce the proportion of central failures within the high-dose radiation region. We will explore whether this appears to be the case by comparing this proportion to prior dose escalation studies based on conventional MRI planning alone.

Response rates - The proportion of complete, partial and any responders will be calculated along with 95% likelihood ratio confidence intervals using RANO criteria. The proportion of any responders will also be compared to published values from historical controls.

11.3 Secondary objective: Assess the ability of pre-therapy and week 3 MET PET scans and advanced MRI to determine sub-volumes at high risk of recurrence.

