11.5 Secondary objective: To assess the ability of post-treatment advanced MRI to distinguish true progression from pseudoprogression

Patients will undergo follow-up advanced MRI (including high b-value MRI) within 1-4 months after completion of chemoradiation. Pseudoprogression is the appearance of progression later determined to be treatment effect, rather than actual progression, and typically occurs within the first 3 months after chemoradiation. True progression status at 12 months will be centrally reviewed by a team of neuro-oncologists, neurosurgeons, neuro-radiologists and radiation oncologists. This gold standard assessment at 12

months will identify patients as 'progressors' or 'non-progressors'. There are several ways to analyze this data. In the first, we will simply assess to what extent the advanced MRI imaging metrics obtained shortly after treatment (1-4 months) can predict the true progression status at 12 months. Because there is little uncertainty surrounding patients who have not progressed at 12 months, the second analysis will only involve apparent 'progressors' at 12 months. The outcome will still be the true (or at least gold standard) assessment of progression status at 12 months and the predictors will again be advanced MRI metrics obtained shortly after treatment. This analysis will directly assess the extent to which the advanced MRI imaging can distinguish 'true' from 'pseudo' progressors. Standard ROC type metrics will be reported, including AUC, sensitivity, specificity as well as negative and positive predictive value for defined thresholds. The key metric from the high b-value MRI and perfusion is the quantity of 'abnormal volume'. Although multiple thresholds will be studied we will consider less than 1 cc abnormal volume on 3 month follow-up high b-value MRI and perfusion to be indicative of pseudoprogression whereas >1 cc abnormal volume will be considered indicative of true progression. While of great clinical interest, the proposed study is not powered to provide definitive answers to these questions and these analyses will be hypothesis generating.

11.6 Secondary objective: To provide descriptive data regarding neuro-cognitive function, health-related quality of life and symptoms related to radiation dose received.

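### Does the plan need to say in 11.2 whether a patient later judged a pseudoprogressor counts as a PFS event?

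*Combined protocol and SAP*

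**What the plan says.** Section 11.2 gives the endpoint: "Progression Free Survival is defined as the time from study enrollment till the first of death from any cause or progression". It adds that "we will compare the observed PFS at 6 months and 1 year to published values from historical control patients". It does not say which assessment of progression is meant.

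Section 10.5.4 is the only place that sets out what progression is: "Progression (PD) is defined by any of the following". The list covers a 25% or greater increase in enhancing lesions on stable or rising steroids, T2/FLAIR increase, new lesions, non-measurable disease and clinical deterioration. Section 10.4.1 points forward to it: "Patients who have tumor progression, as defined below, will not be removed from the protocol". The opening of 10.5 says "Standard RANO criteria will be used primarily to evaluate objective tumor response", with formal reads at "approximately 1 month, 3 months, 7 months, and 13 months after chemoradiation".

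Section 11.5 describes pseudoprogression as "the appearance of progression later determined to be treatment effect, rather than actual progression", which "typically occurs within the first 3 months after chemoradiation". A multidisciplinary team is to settle true progression status at 12 months. That status is the outcome against which the early advanced-MRI measures are tested, in analyses the section itself labels hypothesis generating.

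**The concern.** The plan expects some apparent progressors not to be true ones, yet 11.2 is silent on what happens to their PFS events. Read literally, a patient whose enhancement rises by 25% at the month-3 read is a PFS event on that date, even if the 11.5 review later attributes the change to treatment. Another analyst might take 11.5 as removing that event. Counting the patient lowers PFS and excluding the patient raises it.

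If the choice were made after the data were seen, the comparison with published PFS at 6 months and 1 year could be tilted. The timing makes this a practical question, because early treatment effect would usually be read before the 6-month landmark.

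**Working it through.** **Which definition governs PFS**

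| Place | What it provides | Stated use |
|---|---|---|
| 10.5.4 | Operational criteria, any one sufficient | Evaluation criteria and endpoints; 10.4.1 refers to it |
| 11.5 | Status at 12 months from team review | Outcome for the advanced-MRI predictors |
| 11.2 | Time to progression or death | PFS, no cross-reference |

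Only 10.5.4 can yield an event with a date at any visit. The 11.5 review yields a status at one time point, and no section says it removes or re-dates a PFS event. The ordinary reading is PFS per 10.5.4.

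**Which patients are affected**

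The enhancement and new-lesion criteria carry no treatment-effect exception. The clinical criterion does exclude causes other than the tumor. The T2/FLAIR criterion excludes comorbid events, a term left undefined. A pseudoprogressor flagged only on one of those two is not clearly counted, so the ambiguity is narrower than all pseudoprogressors.

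**Timing**

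Days from enrolment to a read = L + 42 + 28k + w. Here 42 days is the six weeks of radiotherapy, one month is 28 days, and w is the visit window of up to +14 days (10.2, footnote a). L is the lag to the start of radiotherapy. It is not given and is assumed to be 0 to 28 days. For k = 3:

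- w = 0: 126 to 154 days
- w = +14: 140 to 168 days

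Both ranges fall before 6 months (182.6 days). Interruptions or delays could lengthen them.

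**Size**

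The inputs are 40 patients at this center and 80 jointly (11.1). With complete follow-up, one reclassified patient who is otherwise event-free at the landmark shifts PFS by 1/n:

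- 1/40 = 2.5 points
- 1/80 = 1.25 points

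A patient who truly progresses or dies before the landmark shifts it by 0.

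The 95% half-width is 1.96·√(p(1−p)/n), in points:

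| n | p = 0.3 or 0.7 | p = 0.4 or 0.6 | p = 0.5 |
|---|---|---|---|
| 40 | 14.2 | 15.2 | 15.5 |
| 80 | 10.0 | 10.7 | 11.0 |

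The number of patients needed to match that half-width is the half-width (as a proportion) times n:

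- n = 40: 5.7 to 6.2, so 6 or 7 patients
- n = 80: 8.03 to 8.77, so 9 patients

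The denominator is not exact. If 10% were lost, as 11.1 allows for the primary endpoint, the step becomes 1/36 = 2.8 or 1/72 = 1.4 points, and the half-width widens too. If the unboosted patients kept on study under 6.1 are additional to the 40 or 80, each step is smaller.

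The plan states no PFS rate, PFS power or pseudoprogression rate, so there is no figure of its own to reproduce.

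**The case for a change.** The strongest case for a change has four parts.

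- **The shift is systematic.** It goes in one direction, a confidence interval does not capture it, and a sentence could prevent it.
- **Two centers are pooled.** They work under separate protocols, so an unwritten rule might be applied differently at each. Patterns of failure could inherit the difference.
- **Naming standard RANO does not settle it.** That text is tied to response, its content cannot be checked from these documents, and it could not say whether this trial's own 12-month review overrides an earlier call.
- **A remedy exists on paper.** PFS could be reported twice, once per 10.5.4 and once with progression confirmed by the 11.5 review.

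The silence in 11.2 is real, and the one-directional nature of the shift stands. The rest is weaker. Reading 11.5 as deleting PFS events rests on little more than its description of pseudoprogression. The documents do not give the historical progression definitions, so it cannot be shown that either reading makes the comparison wrong.

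The second estimate is also not clearly better. The review gives a status at 12 months rather than a verdict and date for each event. A patient with early treatment effect and true progression at month 9 would simply be a progressor. The review cannot confirm later events, although progression is followed for up to 5 years (10.2, footnote g). Dating events to the first suggestive finding could also move some of them earlier than the 10.5.4 threshold. Finally, the review is not stated to be blinded. The double estimate would need a new event-level adjudication, which is more than a wording change.

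**Conclusion.** No change is called for. This is a missing cross-reference that an analyst would fill sensibly by using 10.5.4. That reading also gives the lower of the two trial figures as long as true events keep their dates, so it does not flatter the regimen.

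The consequence is confined to secondary summaries: 2.5 or 1.25 points per affected patient, and less than the 95% half-width unless at least 6 of 40 or 9 of 80 patients are affected. A one-line pointer in 11.2 would do no harm, but the plan as written is not shown to give a wrong result without it.

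This rests on complete follow-up to the landmark, denominators of 40 and 80, PFS between 30% and 70%, and 10.5.4 being the definition applied. The documents give no pseudoprogression rate and none is assumed, so a larger total shift cannot be excluded. Even then it would bear on a comparison with no decision rule, and the 12-month survival test would be unaffected.

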11.0 STATISTICAL CONSIDERATIONS

This is a study of concurrent temozolomide and high dose radiation using biologic based target volume definition in patients with newly diagnosed glioblastoma (GBM).

The overall goal of this study is to determine if the treatment regimen described in this protocol is sufficiently promising to advance to a definitive randomized trial. Treatment for patients treated under this protocol will differ from standard care in the following ways:

- 1) High b-value diffusion-weighted and perfusion MRI will be used in target volume definition
- 2) The radiation dose to the boost volume will be 75 Gy based on earlier data demonstrating the safety and potential efficacy of this approach.
- **11.1** Primary objective: To improve overall survival at 12 months compared with published historical controls.

The final test addressing this aim will occur when the last enrolled patient completes 12 months of follow-up. If patients drop out or are lost to follow-up prior to 12 months, we will utilize the Kaplan-Meier approach to estimate OS at 12 months. Otherwise we will use the simple binomial proportion of patients who are alive within 12 months of treatment. We will test the null hypothesis that the true 12 months OS is equal to 0.65, based on recently reported survival rates from RTOG 0525 and RTOG 0825. The alternative hypothesis will be that 12 months OS is greater than 0.65. The test will be one-sided at an alpha=0.10 level. We will additionally use the Kaplan-Meier approach to estimated OS over time for all patients and according to MGMT and IDH1 status.

For example, MGMT status is an established prognostic factor in this setting with hazard ratios of approximately 2 for an endpoint of overall survival. On average we would expect a similar proportion of methylated patients in this trial as was observed for RTOG 0525 and RTOG 0825 (30%). However, with a sample size of 40, it is possible that the proportion of methylated patients will differ from 30% by a non-negligible amount. To account for this in the statistical analysis, we will weight patients so that the

weighted proportion of methylated patients is equal to 30%. Specifically, if p* denotes the observed proportion of methylated patients in this trial, the new weights will be .3/p* for methylated patients and (1-.3)/(1-p*) for unmethylated patients.

Sample size considerations:

We anticipate enrolling 40 patients eligible to undergo a boost of radiation (>1 cc combined high b-value DW-MRI and perfusion MRI abnormality) at our institution. A similar protocol will be opened at a second center and treat an additional 40 patients in an identical fashion. This approach was chosen over a single multi-institutional trial protocol for logistical and financial reasons. Nevertheless, we expect to jointly analyze the data from all 80 patients following trial completion. Center will be included as a stratification variable in the analyses. Allowing for 10% of these patients to be non-evaluable for the primary endpoint, 40 (80) enrolled patients will provide greater than 80% power to detect an improvement in 12 month OS from 65% (based on historical controls) to 82% (40 patients) or 78% (80 patients). These results are based on an exact 1-sided test at alpha=0.10. Once completed, this trial will determine if the treatment is sufficiently promising to warrant further investigation in a multi-center, randomized trial.

11.2 Secondary objective: To estimate progression-free survival, patterns of failure and response rates in relation to values from historical control patients.

Progression Free Survival is defined as the time from study enrollment till the first of death from any cause or progression. Kaplan-Meier estimates of PFS will be generated for all patients on this trial and according to MGMT/IDH1 status. Additionally we will compare the observed PFS at 6 months and 1 year to published values from historical control patients.

Patterns of failure and response rates - Failures will be classified as central, in-field, marginal or distant, based on previously published criteria. Our hypothesis is that including high b-value diffusion and perfusion MRI in treatment planning will reduce the proportion of central failures within the high-dose radiation region. We will explore whether this appears to be the case by comparing this proportion to prior dose escalation studies based on conventional MRI planning alone.

Response rates - The proportion of complete, partial and any responders will be calculated along with 95% likelihood ratio confidence intervals using RANO criteria. The proportion of any responders will also be compared to published values from historical controls.

11.3 Secondary objective: Assess the ability of pre-therapy and week 3 MET PET scans and advanced MRI to determine sub-volumes at high risk of recurrence.

Several approaches are possible, ranging from very ad hoc qualitative analysis to complex voxel level image analysis. Here we describe an empiric approach to assessment of the ability of an image to predict volumes at highest risk of recurrence. The goal is to compare the probability of the imaging defined subvolume recurring with the probability of the rest of the tumor recurring. This comparison must take into account two potential confounding variables. First, these two (absolute) volumes will typically be different for a given patient and thus any analysis regarding location of recurrence must be weighted by volume. Second, the imaging defined volume may receive higher (or lower) dose than the rest of the tumor. One means to do this is to stratify the analysis on dose received. For example, assume we categorize the initial PTV in terms of high-dose and low-dose regions. Then for each region (strata) we could compute the following quantities

- 1) P1=Proportion of the imaging sub-volume overlapping with recurrence volume (rVOI)
- 2) P2=Proportion of the non-imaging sub-volume overlapping with rVOI

Evidence for success of the imaging at goal to 'determine tumor sub-volumes at high risk of recurrence' would be given when P1>P2. Across the population of patients, we could perform a stratified test whether E[P1] > E[P2]. Metrics such as sensitivity and specificity will be used to quantify the spatial predictive ability and will be calculated as proportions of volumes. For example, for sensitivity we will calculate the proportion of the rVOI contained in the imaging subvolume. Predictive values (PPV and NPV) could be calculated in a similar manner.

Summary statistics will also be generated describing the volumes of each of these imaging defined sub-volumes and their overlap.

11.4 Secondary objective: To prospectively compare tumor volumes defined by baseline MET PET with baseline high b-value DW-MRI and perfusion MRI A conformality index⁴² will be calculated that compares the MET-PET defined tumor volume with high b-value DW-MRI and perfusion MRI defined tumor volume. Non-overlapping regions of MET-PET tumor volume and MRI tumor volume as well as the overlapping regions will be calculated for each patient and used to calculate conformality indices. Assuming the endpoint is normally distributed, the 95% confidence interval for the mean has half-width = 1.96*Standard error of the mean.

11.5 Secondary objective: To assess the ability of post-treatment advanced MRI to distinguish true progression from pseudoprogression

Patients will undergo follow-up advanced MRI (including high b-value MRI) within 1-4 months after completion of chemoradiation. Pseudoprogression is the appearance of progression later determined to be treatment effect, rather than actual progression, and typically occurs within the first 3 months after chemoradiation. True progression status at 12 months will be centrally reviewed by a team of neuro-oncologists, neurosurgeons, neuro-radiologists and radiation oncologists. This gold standard assessment at 12

months will identify patients as 'progressors' or 'non-progressors'. There are several ways to analyze this data. In the first, we will simply assess to what extent the advanced MRI imaging metrics obtained shortly after treatment (1-4 months) can predict the true progression status at 12 months. Because there is little uncertainty surrounding patients who have not progressed at 12 months, the second analysis will only involve apparent 'progressors' at 12 months. The outcome will still be the true (or at least gold standard) assessment of progression status at 12 months and the predictors will again be advanced MRI metrics obtained shortly after treatment. This analysis will directly assess the extent to which the advanced MRI imaging can distinguish 'true' from 'pseudo' progressors. Standard ROC type metrics will be reported, including AUC, sensitivity, specificity as well as negative and positive predictive value for defined thresholds. The key metric from the high b-value MRI and perfusion is the quantity of 'abnormal volume'. Although multiple thresholds will be studied we will consider less than 1 cc abnormal volume on 3 month follow-up high b-value MRI and perfusion to be indicative of pseudoprogression whereas >1 cc abnormal volume will be considered indicative of true progression. While of great clinical interest, the proposed study is not powered to provide definitive answers to these questions and these analyses will be hypothesis generating.

11.6 Secondary objective: To provide descriptive data regarding neuro-cognitive function, health-related quality of life and symptoms related to radiation dose received.

Patients will complete neurologic exam, mini mental status exam and EORTC global QOL questionnaire and specific brain module and MDASI-BT before, during and after treatment. The results will be summarized descriptively over time as well as by radiation dose. The relation between these outcomes and survival will be assessed by using QOL numbers as (possibly time dependent) predictors in a Cox regression model. Every effort will be made to avoid missing data. Missing data will be carefully considered as to whether it is missing at random or not. Mixed models with subject level random effects can provide valid estimation and inference under certain patterns of informative missingness and will be utilized where warranted. We will also perform simple checks whether for example subjects with decreased QOL are more likely to drop out. For example, we will compare observed QOL at time t amongst patients who did or did not drop out (i.e. decline to provide QOL data) by time t+1.

11.7 Interim analysis:

Due to a possible increased incidence of grade 3 or higher CNS toxicity (possibly, probably, or definitely related to treatment), we will analyze the data 6 months after the 20th patient completes radiation. At this point approximately 29 patients, out of the planned total of 40 patients eligible for radiation boost, will have been enrolled on the trial. It is possible that 6 patients will experience toxicity prior to this time point, in which case, the trial would be halted as soon as the 6th patient experiences toxicity. If the number of patients, out of the first 20, with toxicity (as defined above) is 6 or greater, the trial will be stopped due to possible safety concerns. The operating characteristics of this stopping rule are given in Table 1 below. When the true toxicity rate is 10%, just

1% of trials will stop early. On the other hand, if the probability of toxicity is 40%, 87% of trials will stop early. We note here that we do not expect to see excessive toxicity in this study because the volume of brain treated with the experimental (boost) dose of radiation will be limited to 1/3 the volume of brain, shown to be safe based on our prior dose-escalation study based on standard MRI alone.³⁰

Table 1. The proportion of trials stopping

True P(tox)	10%	20%	30%	40%
Proportion of	1%	20%	58%	87%
Trials				
Stopping				
Early				

